9.4.2 Identity of Investigational Product

E2609 tablets of 5-, 10-, and 25-mg dose strengths will be supplied. Placebo tablets of identical appearance will also be available. Each subject will receive 2 tablets, which combined will make up the required doses of E2609 5, 15, 50 mg, or placebo. The tablets will be supplied by the Sponsor in labeled blister packs. The product release certificates for E2609 and placebo will be included in the clinical study report for this protocol.

Subjects will be stratified and randomized, and drug will be dispensed, via an interactive voice and web response system (IxRS) system (see [Section 9.4.3](#)).

The sponsor will provide the study drugs packaged in a double-blind configuration. Each subject's study tablets will consist of either E2609 or placebo, or both (see [Section 9.4.2.3](#) for labeling details).

9.4.2.1 Chemical Name and Formula of E2609

- Test drug code: E2609
- Generic name: not applicable
- Chemical name: International Union of Pure and Applied Chemistry
- *N*-{3-[(4*aS*,5*R*,7*aS*)-2-Amino-5-methyl-4*a*,5-dihydro-4*H*furo[3,4-*d*][1,3]thiazin-7*a*(7*H*)-yl]-4-fluorophenyl}-5-(difluoromethyl)pyrazine-2-carboxamide
- Molecular formula: C₁₉H₁₈F₃N₅O₂S
- Relative molecular mass: 437.44

9.4.2.2 Comparator Drug

Not applicable.

9.4.2.3 Labeling for Study Drug

E2609 will be labeled in accordance with text that is in full regulatory compliance with each participating country and is translated into the required language(s) for each of those countries. The following information may be included but is not limited to:

- Protocol number
- For clinical study use only
- Name and address of the sponsor
- Chemical name/drug identifier (ID)

- Lot number/batch number
- Storage conditions, expiration date if necessary

9.4.2.4 Storage Conditions

Study drug will be stored in accordance with the labeled storage conditions. Temperature monitoring is required at the storage location to ensure that the study drug is maintained within an established temperature range. The investigator or designee (or if regionally required, the head of the medical institution) is responsible for ensuring that the temperature is monitored throughout the total duration of the study and that records are maintained; the temperature should be monitored continuously by using either an in-house validated data acquisition system, a mechanical recording device, such as a calibrated chart recorder, or by manual means, such that minimum and maximum thermometric values over a specific time period can be recorded and retrieved as required.

9.4.3 Method of Assigning Subjects to Treatment Groups

Subjects will be assigned to treatments based on a computer-generated randomization scheme. The randomization scheme and identification for each subject will be included in the final clinical study report for this study. The doses and number of treatment groups to be used for Stage A (all subjects), for Stage B MCI/Prodromal subjects and Stage B for mild to moderate AD subjects are described in [Section 9.4.1](#). (revised per Amendment 01)

Randomization will be performed centrally by an IxRS. The IxRS or clinical supply vendor will generate the randomized blister card identification numbers. At enrollment, the investigator or designee will call the IxRS to register the subject information. At randomization (Visit 3), the IxRS will assign each subject a unique randomization number.

9.4.4 Selection of Doses in the Study

It is not known how the level of CSF or brain A β reduction is related to clinical efficacy. Therefore, in this study, doses will be selected such that at steady state, they will result in 25%, 50%, and 75% reduction in CSF A β levels from baseline to cover a broad range of PD effects.

In Study 007, the relative bioavailability of a tablet formulation of E2609 in the fed and the fasted states compared with the capsule formulation in the fasted state (used in Studies 001 and 002) was investigated. It was found that when the tablet form of E2609 (50 mg) was administered with food, the exposure (ie, AUC) of the parent drug E2609 was higher, with lower maximum observed concentrations and reduced exposure to the metabolites, compared with either formulation in the fasted state.

Based on the PK/PD modeling using data from healthy volunteer Studies 001, 002, and 007, doses of 5, 15, and 50 mg QD administered as the tablet formulation with food in this study should achieve CSF A β reduction from baseline of approximately 25%, 50%, and 75% at steady state, respectively ([Table 3](#)).

Table 3 Predicted Steady State Plasma PK Parameters and CSF Amyloid β Reduction From Baseline

| E2609 Tablet Daily Dose (mg) With Food | E2609 Plasma $C_{max,ss}$ (ng/ml) | E2609 Plasma $C_{ss,av}$ (ng/ml) | E2609 Plasma $AUC_{(0-24h)ss}$ (ng.h/ml) | % Reduction CSF BACE1 Activity | % Reduction CSF $A\beta(1-x)$ |
|--|-----------------------------------|----------------------------------|--|--------------------------------|-------------------------------|
| 5 | 6.2 | 3.3 | 80.3 | 16.2 | 33 |
| 15 | 18.6 | 10 | 240.9 | 36.6 | 56 |
| 50 | 62.1 | 33.5 | 803.0 | 65.7 | 79 |

$A\beta(1-x)$ = amyloid beta monomer from amino acid 1 to x, $AUC_{(0-24h)ss}$ = area under the concentration x time curve at steady state from time zero to 24 hours, BACE1 = beta-amyloid converting enzyme, CSF = cerebrospinal fluid, $C_{ss,av}$ = average steady-state concentration, $C_{max,ss}$ = maximum plasma concentration at steady state, PK = pharmacokinetics.

The PK/PD modeling described above, which was conducted using data obtained from healthy volunteers, has also been supported by modeling of data from subjects with an underlying AD pathology (Study 101). Furthermore, external data with another BACE1 inhibitor (MK-8931) showed a similar PD effect in AD patients as in healthy volunteers (Forman, et al., 2013). Therefore we are confident that the modeling of E2609 effects in healthy subjects will be applicable for both MCI/Prodromal and mild to moderate AD dementia patients. (revised per Amendment 01)

The exposure of the highest dose in this study (50 mg QD tablet administered with food) is less than that of the 100 mg QD dose (capsule administered fasted) in Study 002.

The 100 mg QD dose administered for 14 days in Study 002 was well tolerated with no clinically significant changes in laboratory parameters, vital signs, or ECG parameters. On Day 15, for the 100 mg QD cohort in Study 002, there was a reduction of CD4 lymphocyte counts compared with placebo (CD4 lymphocyte counts on E2609 decreased by 3.1% from baseline, whereas the placebo control showed an increase of 8.7%), but this decrease was less than that observed at doses of 200 mg (22.9% decrease) or 400 mg (17.3% decrease). No subject had infections or drug rash while receiving E2609 100 mg QD or at lower doses in Study 002, whereas at 200 and 400 mg QD, 4 subjects had symptomatic orolabial HSV1 relapses and 2 subjects at the highest dose had drug rash. The highest dose for Study 202 of 50 mg QD (tablet administered with food) is therefore expected to have a similar or better safety profile compared with the 100 mg QD capsule (administered fasted) in Study 002. Specific exclusion criteria, blinded and unblinded safety monitoring procedures, and safety criteria for discontinuation from study drug are included in this study in order to mitigate any immunology-related risk with E2609, particularly in light of the progression from 14 days of dosing (Study 002) to 18 months of dosing in this study.

In Stage A, all subjects will be randomized to receive either placebo or E2609 at 5, 15, or 50 mg QD. In Stage B, subjects in the MCI/Prodromal cohort will continue to be randomized to receive either placebo or E2609 at 5, 15, or 50 mg QD. In Stage B, subjects in the Mild to Moderate AD cohort will be randomized to receive either placebo or E2609 at 15 or 50 mg QD, but not the 5-mg QD dose. The rationale for not including an E2609 5-mg QD dose in the dose regimens for Stage B subjects with mild to moderate AD is that more

advanced disease may require greater reduction in CSF A β levels for comparable effects. (revised per Amendment 01)

Interim analyses of the E2609 plasma PK for all subjects and the E2609CSF PK and PD profiles will be performed on baseline data and samples collected after at least 4 weeks of study drug. These interim analyses, as well as analyses of safety data, will be performed on an ongoing basis throughout Stage A. Refer [Section 9.7.3](#) for more detail. The median and mean percentage change from baseline in CSF A β (1-x) measured after 4 weeks of treatment for each dose of E2609 and its 90% confidence interval for the median will be derived. In addition, exploratory PK/PD modeling will be conducted. This PK/PD modeling will use the observed PK and PD data from Stage A and will relate the average steady state plasma concentration of E2609 to steady state CSF A β (1-x) percentage reduction from baseline after 4 weeks of dosing. (revised per Amendments 01, 02, 03, and 04)

If dose adjustment is required for Stage B, a protocol amendment reflecting the new doses will be submitted.

9.4.5 Selection and Timing of Dose for Each Subject

E2609 is administered orally, QD, with food. Study treatment will begin on Day 1 following randomization and will continue for approximately 78 weeks.

9.4.6 Blinding

E2609 and placebo will be administered as tablets of identical appearance.

During the Randomization Phase and Follow-Up Phases, subjects, caregivers/informants, and all clinical site personnel involved with the conduct and interpretation of the study, including investigators will be blinded to the treatment codes (double-blind). In order to make decisions about the remainder of the study as well as the full E2609 clinical development program, the sponsor will unblind safety, PK, and PD data on an ongoing basis and perform interim analyses of these data. (revised per Amendment 03)

Every effort should be made to keep the site staff responsible for reviewing laboratory reports and assessing AEs separate from the site staff responsible for the efficacy assessments, particularly for the CDR (ie, those who are trained and certified to perform the various cognitive assessments that are undertaken in this study). Furthermore, at the site, the notes and reports relating to safety assessments must be kept separate from the notes and reports relating to efficacy, particularly for the CDR. (revised per Amendment 01)

Randomization data will be kept strictly confidential, filed securely by an appropriate group with the sponsor or CRO and accessible only to authorized persons (eg, Eisai Global Safety) until the time of unblinding, per the standard operating procedure.

The PK/PD interim analyses will take place throughout the study as per Amendment 03 and will be conducted by an independent PK/PD scientist at the sponsor. Any additional changes to dose required for this study will be reflected in a further amendment to the protocol and the Statistical Analysis Plan will detail how data will be handled in the primary analysis. (revised per Amendments 02 and 04)

In the event that emergency conditions require knowledge of the study treatment given, the blind may be broken via the code breaker facility within the IxRS. Emergency procedures for revealing drug codes are given in [Section 9.5.4.5](#). If possible, before breaking the blind, the investigator should consult with the sponsor to ascertain the necessity of breaking the code.

At the conclusion of the study, all unused drug supplies are to be returned to the Eisai approved contract packaging vendor.

9.4.7 Prior and Concomitant Therapy

Medication (including over-the-counter medications) or therapy administered to the subject before the study (within 6 months of randomization) and during the study (starting at the date of informed consent) will be recorded on the Prior & Concomitant Medication eCRF or Non-Pharmacological Procedures eCRF. The investigator will record on the Adverse Event eCRF any AE for which the concomitant medication/therapy was administered. If the concomitant medication/therapy is being administered for a medical condition present at the time of entry into the study, the investigator will record the medical condition on the Medical History and Current Medical Condition eCRF.

Listings of prohibited and permitted drugs are provided in [Appendix 2](#). Prohibited medications are presented in [Listing 1](#) through [Listing 5](#). Medications that are permitted with restrictions are listed in [6](#) through [Listing 8](#). (revised per Amendment 04)

The following agents are not permitted before randomization (specific timeframes are shown below) and throughout the study until after the last treatment visit: (revised per Amendment 04)

- Drugs which may cause QTc prolongation are not permitted for a period of 5 half-lives or 14 days (whichever is longer) before randomization
- Strong CYP3A4 inhibitors are not permitted for a period of 5 half-lives or 14 days (whichever is longer) before randomization
- Live vaccines are not permitted within 3 months before randomization. This does not apply to non-live/inactivated vaccines
- Ig therapy and biologic drugs are not permitted within 6 months before randomization

- Systemic or ocular immunosuppressive or immunomodulatory drugs are not permitted for a period of 5 half-lives or 60 days (whichever is longer) before randomization. However, during the treatment period of the study, short term (not more than 14 days) use of steroids up to the equivalent of prednisolone 40 mg once daily is permitted after discussion with the Medical Monitor. Dosing with study drug should be suspended from the time steroid treatment is started. Complete blood count and lymphocyte subsets should be determined prior to starting steroid treatment and continue to be monitored weekly. Study drug may be resumed after discussion with the Medical Monitor when the following conditions are met: (1) treatment with steroids has been completed for at least 1 week; (2) total lymphocytes not <LLN; (3) no lymphocyte subsets are below the discontinuation threshold; (4) the investigator considers that the medical condition which required treatment with steroids has improved or resolved. Weekly testing of lymphocyte subset counts and CBC with differentials is required for 4 weeks following resumption of study drug administration. (revised per Amendment 04)

Subjects taking AChEIs or memantine must meet the following criteria in order to be included in the primary analyses:

- On a stable dose for 12 weeks before the Baseline cognitive assessments at Visit 2
- Remain on a stable dose while on study

Subjects who initiate treatment with an AChEI or memantine during the study, or who change their dose of AChEI or memantine while on study, will be allowed to continue in the study, but their clinical efficacy data will be censored from the time of drug initiation for the primary analyses.

Subjects taking all other non-prohibited concomitant medications must meet the following requirements:

- Must be on stable dose for at least 4 weeks before randomization, except for medications that are administered as short courses of treatment or which are to be used intermittently as needed. Subjects who are on anticoagulants may have a variable dose but should have stable anticoagulation control for at least 4 weeks before randomization. They may be required to stop their anticoagulant medication prior to CSF collection and then restart this medication after the LP procedure, as per local guidelines. (revised per Amendment 04)
- Medications that are used as needed, rather than on a stable daily basis, and which are central nervous system (CNS) active and may affect cognitive function, are not permitted during a period of 72 hours before cognitive testing

Subjects who initiate treatment with or have dose adjustment of drugs not intended for treatment of cognitive impairment during the study may continue in the study if in the opinion of the investigator this will not interfere with study procedures or subject safety, and are not prohibited above. If the subject initiates treatment for co-morbidities with a (non-prohibited) drug that may affect cognitive function, the subject should not have cognitive assessments performed until the dose has been stable for at least 4 weeks.

Antiplatelet therapy: (revised per Amendment 04)

- For subjects who consent to CSF sample collection: Either aspirin or clopidogrel (or any other antiplatelet drug which is not aspirin) are permitted in all subjects. Aspirin and clopidogrel (or any other antiplatelet drug which is not aspirin) in combination are also permitted but subjects who are on such a combination of antiplatelet drugs may be required to stop 1 or more of these antiplatelet drugs before the LP procedure and restart after the LP as per local guidelines.
- For subjects who do not consent to CSF sample collection: Aspirin and clopidogrel, individually or in combination, are permitted.

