- a. A study drug discontinuation threshold will be set based on absolute counts of CD4 (T helper cells), CD8 (cytotoxic T cells), or CD19 (B cells). The discontinuation threshold will be set at below the level of the population-adjusted LLN (CD4=396 cells/ μ L; CD8=157 cells/ μ L; and CD19=74 cells/ μ L), at a level that represents a greater risk of opportunistic infection in the treated population. (revised per Amendment 02) For CD4 (T helper cells) the discontinuation threshold is 250 cells/ μ L. For CD8 (cytotoxic T cells) and CD19 (B cells) the discontinuation thresholds are 150 cells/ μ L and 50 cells/ μ L, respectively. Any subject who has CD4 (T helper cells), CD8 (cytotoxic T cells), or CD19 (B cells) absolute counts below the discontinuation threshold as confirmed by a repeat test conducted within 1 week of the initial test but who has no clinical signs or symptoms of infection, will have study drug temporarily suspended for at least 2 weeks but no more than 4 weeks. During this period of study drug suspension, lymphocyte subset counts and complete blood count (CBC) with differentials will continue to be tested weekly until CD4 (T helper cells), CD8 (cytotoxic T cells), and CD19 (B cells) have all returned to greater than the population-adjusted LLN after which time study drug can be resumed. Testing of lymphocyte subset counts and CBC with differentials is required weekly for 4 weeks following resumption of study drug administration. Temporary suspension and rechallenge with study drug is only permitted once for any given subject. If the lymphocytes and CD counts do not return to greater than the population-adjusted LLN within 4 weeks from the start of temporary suspension the subject will need to be permanently discontinued from study drug. (revised per Amendment 04)

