- b. Subjects with CD4 (T helper cells), CD8 (cytotoxic T cells), or CD19 (B cells) absolute counts between the population-adjusted LLN and the discontinuation threshold will have lymphocyte subset counts performed on a weekly basis. (revised per Amendments 02 and 04) During the early stages of the treatment period, where visits are conducted weekly (ie, Visits 4, 5, 6, and 7), lymphocyte subsets are already scheduled to be measured on a weekly basis and so additional visits or blood draws are not required. (revised per Amendment 02) For these subjects, the decision as to whether the subject remains on study drug or is to be discontinued from study drug will be based upon clinical judgment and will take into account any clinical presentation in addition to the lymphocyte subset counts. These subjects may continue with treatment if there is no clinical evidence of infection. They will be discontinued from study drug if they have infections of a moderate to severe intensity (eg, subjects whose infections are not localized, or are systemically unwell, or who require systemic anti-infective drug treatment).

Table 1 Study Drug Actions for Lymphocyte Subset Absolute Counts

| Lymphocyte subset absolute counts | Action | Decision to continue, discontinue, or temporarily suspend study drug |
|---|--|--|
| CD4 (T helper cells), CD8 (cytotoxic T cells), or CD19 (B cells) absolute counts below discontinuation threshold and no clinical signs or symptoms of infection | Retest within 1 week along with CBC with differentials | If retest performed within 1 week confirms lymphocyte subset counts below the discontinuation threshold, temporarily suspend study drug for between 2 and 4 weeks. Continue weekly testing of lymphocyte subsets and CBC with differentials. Rechallenge with study drug allowed when CD4 (T helper cells), CD8 (cytotoxic T cells), and CD19 (B cells) absolute counts all greater than population-adjusted LLN. Temporary suspension and rechallenge permitted only once for each subject. |
| CD4 (T helper cells), CD8 (cytotoxic T cells), or CD19 (B cells) absolute counts between population-adjusted LLN and discontinuation threshold | Lymphocyte subset counts (and CBC with differentials) to be performed weekly until lymphocyte subset counts return to \geq population-adjusted LLN | Decision will be based upon lymphocyte subset counts and clinical judgment |

LLN = lower limit of normal, CBC = complete blood count.

(Table revised per Amendments 02 and 04)

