9.4 Treatments

9.4.1 Treatments Administered

For this study the test drug is E2609 and the control drug is placebo. All study drugs are to be administered orally, QD, with food.

Treatments to be administered in Stage A and Stage B are shown below and in [Figure 1](#).

The 2 highest E2609 doses (15 and 50 mg) taken into Stage B, after the PK/PD and safety review from Stage A, will be used for the mild to moderate AD population in Stage B. (revised per Amendment 01)

- Stage A: 3 doses (5, 15, and 50 mg) of E2609 or placebo
- Stage B, MCI/Prodromal Cohort: 3 doses (5, 15, and 50 mg) of E2609 or placebo
- Stage B, Mild to Moderate AD Cohort: 2 doses (15 and 50 mg) of E2609 or placebo. (revised per Amendment 01)

Study treatment will begin on Day 1 (at the study site) following Randomization and will continue for approximately 78 weeks. Please refer to [Table 7](#) and [Section 9.5.1.4.1](#) for specific information on drug administration on days when PK sampling is to be performed.

Study drug doses will remain the same for each individual subject unless the interim PK/PD analysis determines that an entire dose level requires adjustment ([Section 9.4.4](#)). See

[Section 9.3.3](#) for safety-related discontinuation criteria of study drug. If a subject develops a concurrent illness during the treatment period, the investigator should discuss with the medical monitor on whether dosing with study drug needs to be temporarily suspended. As a general clinical guideline, dosing with study drug may be resumed after resolution or stabilization of the concurrent illness, after discussion with the medical monitor.

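### For an uninfected subject on a permitted steroid course with a confirmed count below the discontinuation threshold, Sections 9.3.3(a) and 9.4.7 give opposite answers on restarting study drug

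*Protocol*

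**What the plan says.** **Count-triggered suspension (Protocol Section 9.3.3(a), Table 1).** The trigger is a CD4, CD8 or CD19 count "below the discontinuation threshold as confirmed by a repeat test conducted within 1 week of the initial test" in a subject without signs of infection. "For CD4 (T helper cells) the discontinuation threshold is 250" cells/µL; for CD8 and CD19 it is 150 and 50. Study drug is held for 2 to 4 weeks with weekly testing, until the three subsets "have all returned to greater than the population-adjusted LLN after which time study drug can be resumed". Those limits are 396, 157 and 74 cells/µL. If recovery is not reached "within 4 weeks from the start of temporary suspension the subject will need to be permanently discontinued from study drug". The section adds: "Temporary suspension and rechallenge with study drug is only permitted once for any given subject". Table 1 repeats this: "Temporary suspension and rechallenge permitted only once for each subject".

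**Steroid suspension (Section 9.4.7, repeated in the synopsis and in Appendix 2, Listing 2, footnote b).** Study drug is held when a permitted steroid course of up to 14 days begins, whatever the counts, and subsets are then checked weekly. After Medical Monitor discussion, drug may restart when steroids have been over for a week or more, total lymphocytes are not under the LLN, the treated condition has improved or resolved, and the third condition is met: "3) no lymphocyte subsets are below the discontinuation threshold". No maximum duration is given, and there is no reference to Section 9.3.3(a).

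**Counts between threshold and LLN (Section 9.3.3(b), Table 2).** A subject in this range without infection may stay on study drug.

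**The concern.** The two sections set different recovery levels for restarting the same drug, and one subject can meet both triggers. Section 9.3.3(a) applies to any subject and makes no exception for steroid use. Section 9.4.7 requires the weekly counts that would reveal a low value, and its third condition only has work to do if counts may fall below the threshold. Both texts are marked as revised under Amendment 04, so neither supersedes the other.

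The consequences are unequal and partly irreversible. Section 9.3.3 places the thresholds at a level of greater risk of opportunistic infection, and Section 7.1 reports lymphocyte reductions in the multiple-dose study. Under Section 9.5.5 a subject discontinued early cannot restart. Two identical subjects could therefore be re-exposed or permanently stopped depending on which section was followed, and their exposure and discontinuation data would reflect that reading.

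**Working it through.** No sample-size, power or alpha figure is involved, so the check sets the rules side by side and finds where they disagree.

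| | 9.3.3(a) / Table 1 | 9.4.7 |
|---|---|---|
| Trigger | Confirmed count below threshold, no infection | Start of a permitted steroid course, any count |
| Subset level for restart | CD4 > 396, CD8 > 157 and CD19 > 74 | CD4 ≥ 250, CD8 ≥ 150 and CD19 ≥ 50 |
| Other restart conditions | Held at least 2 weeks | Off steroids at least 1 week; total lymphocytes not under LLN; condition improved or resolved; Medical Monitor discussion |
| Time limit | Permanent stop if not recovered within 4 weeks | None stated |
| Repeats | Once per subject | None stated |

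**Band of disagreement (LLN minus threshold, cells/µL).**
- CD4: 396 − 250 = 146
- CD8: 157 − 150 = 7
- CD19: 74 − 50 = 24

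The subset conditions disagree when all three counts are at or above threshold and at least one is not above its LLN.

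**Case 1: steroid-suspended, never confirmed below threshold, now in a band.** Section 9.3.3(a) is not triggered. Section 9.3.3(b) would allow treatment without infection, and 9.4.7 allows restart. There is no contradiction.

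**Case 2: steroid-suspended, no infection, CD4 confirmed below 250, then CD4 of 300 at week 4.** Assume CD8 and CD19 are above their LLNs and the other 9.4.7 conditions hold. Since 300 ≥ 250, 9.4.7 permits restart. Since 300 < 396, 9.3.3(a) bars restart, and at 4 weeks it requires permanent discontinuation. This is a contradiction.

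**Case 3: sub-threshold count with infection.** Section 9.3.3(c) and Table 2 discontinue the subject, so this case is outside the overlap.

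**The 4-week clock in Case 2.** A full 14-day course plus the 7-day wait takes 14 + 7 = 21 of 28 days. Suppose drug stops for steroids on day 0 and the low count is confirmed on day 14. If the clock runs from the steroid suspension, the limit falls on day 28. If it runs from the count-triggered suspension, it falls on day 14 + 28 = 42. The text does not say which applies when drug was already being held.

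**The case against.** The strongest reply is that 9.4.7 only permits restart, while 9.3.3(a) commands discontinuation. A site that follows 9.3.3(a) breaches nothing in 9.4.7, so only a sentence on precedence is missing. It is true that the stricter path complies with both. But a site that follows 9.4.7 as written breaches 9.3.3(a), and nothing in 9.4.7 warns it.

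A second reply is that restart under 9.4.7 passes through the Medical Monitor, so it does not rest on each site's reading alone. That tempers the worry about variation. It does not settle the conflict: the discussion is an added condition, and it is not said to override 9.3.3(a).

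A third reply is that the single-rechallenge limit sits inside item (a) and Table 1's sub-threshold row, so in context it concerns count-triggered suspensions. That is a fair reading. It still leaves open how the limit applies to a subject suspended for both reasons.

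Three stronger readings are tempting, and the documents do not support them.
- A reader might infer that 9.3.3(a) bars every steroid-suspended subject from restarting below the LLN. It binds only those with a confirmed sub-threshold count, and 9.4.7 asks for more than a subset level.
- A reader might infer a like collision with the concurrent-illness rule in Section 9.4.1, under which "dosing with study drug may be resumed after resolution or stabilization of the concurrent illness, after discussion with the medical monitor". That paragraph already points to Section 9.3.3 for discontinuation criteria and calls its own rule a general guideline, so no collision is shown.
- A reader might infer a separate total-lymphocyte test from the closing sentence of 9.3.3(a), which mentions lymphocytes alongside CD counts. The population-adjusted LLN is defined only for CD4, CD8 and CD19, so this is loose wording.

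**Conclusion.** The contradiction is real but confined to one group: subjects without infection, suspended for a permitted steroid course, with CD4, CD8 or CD19 confirmed below 250, 150 or 50 cells/µL, whose counts then recover to the threshold or above but not all above 396, 157 and 74. For them, 9.4.7 permits restart when its other conditions hold. Section 9.3.3(a) bars it and requires permanent discontinuation at 4 weeks. The zone is widest for CD4 (146 cells/µL), smaller for CD19 (24) and narrow for CD8 (7).

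This rests on reading 9.3.3(a) as written, applying to any subject with no steroid exception. The documents give no frequency for the overlap, so the number of subjects affected cannot be stated. The point merits correction because two stated safety rules conflict and one outcome cannot be reversed.

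**What to change.** Reconcile Section 9.3.3(a), Table 1, Section 9.4.7, the synopsis and Listing 2 footnote b so that together they state:

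1. which restart condition governs a steroid-suspended, uninfected subject who also has a confirmed sub-threshold count;
2. from which day the 4-week limit runs when drug is already being held for steroids;
3. whether a steroid suspension counts toward the single permitted suspension and rechallenge.

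A cross-reference between 9.3.3(a) and 9.4.7 would keep them aligned. This review does not say which threshold or rule is right; that is for the sponsor to decide.

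The cost is wording in one amendment and a notice to sites. No new procedures are needed for this group, because both the steroid and the count-triggered rules already require weekly subset testing. That would not be true of concurrent-illness suspensions under Section 9.4.1, which this change leaves alone.
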